### 7.3 Safety Assessments

Safety will be assessed by:

- AEs and SAEs throughout the entire duration of the study, including detailed assessment of AEs involving the oral cavity.
- Changes from baseline in clinical laboratory test results.
- Changes from baseline in vital signs and weight.
- Change from baseline in MADRS (see [Section 7.2.4](#)).
- Changes from baseline indicative of increased suicidal ideation or behavior as assessed by the C-SSRS.
- Changes from baseline in participant-rated CSFQ-14.

#### 7.3.1 Adverse Event and Prior/Concomitant Medication handling conventions

To handle missing or partial AE and prior/concomitant medication dates, the following rules will be applied.

For partial start dates:

1. If the year is unknown, then do not impute the date but assign a missing value.
2. If the month is unknown, then:
  - a. If the year matches the year of the first dose date, then impute the month and day of the first dose date.
  - b. Otherwise, assign “January.”
3. If the day is unknown, then:
  - a. If the month and year match the month and year of the first dose date, then impute the day of the first dose date.
  - b. Otherwise, assign “01.”

For partial end dates:

1. If the year is unknown, then do not impute the date but assign a missing value.
2. If the month is unknown, then assign “December.”
3. If the day is unknown, then assign the last day of the month.

Adverse events are categorized as either pre-treatment adverse events or treatment-

emergent adverse events based on the response to the CRF question “Did the AE start prior to the first dose?”

After implementing the rules above, to determine whether medications with missing start or stop dates are prior or concomitant medications, the following strategy will be used:

1. If the start date and stop date are both missing, then the most conservative approach is taken and the medication is considered to be a concomitant medication.
2. If the start date is missing but the stop date is not missing and is after the day of first study dose administration, then the most conservative approach is taken and the medication is considered to be concomitant.
3. If the start date is missing but the stop date is not missing and is on or before the day of first study dose and after the date of signed informed consent, then the medication is considered to be a prior medication.
4. If the start date is not missing but the stop date is missing, then the most conservative approach is taken and medication is considered to be concomitant (assuming that the start date is prior to ten days after last dose).

The missing severity of an AE will be imputed to “severe”; the missing relationship to study drug of an AE will be imputed to “related”.

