11.3.1. Adverse Events (AEs)

Patients will be monitored for AEs throughout the study from the time that the patient signs an informed consent and onward. AEs that are spontaneously reported, elicited or observed are to be recorded on the CRF with the date, time of onset, date and time of resolution, severity, seriousness, causality (relationship to study medication), actions required, and outcome.

To elicit AEs, non-leading, simple questions with minimal connotations should be used as the initial questions at all evaluation points during the study. Examples of these questions can be:

- How have you felt since your last visit?
- Have you had any health problems since your last visit?

If an AE occurs, the investigator will institute support and/or treatment as deemed appropriate. If a non-serious AE is unresolved on the last day of the study, an effort should be made to follow up until the AE is resolved or stabilized, the patient is lost to follow-up, or there is some other resolution of the event.

There are many symptoms associated with PTSD that can vary in intensity and frequency over time. Only symptoms that significantly worsen or become more frequent, in the opinion of the patient and outside of their normal experience, should be reported as an adverse event.

If a patient reports an oral cavity adverse event, the Investigator should examine the oral cavity to confirm the presence or absence of any irritation or other signs. Additional details related to onset, duration, severity and reversibility of the oral cavity event will be documented (Section 11.3.5).

Additional information regarding definition and reporting requirements for adverse events, serious adverse events, and pregnancies is provided in [Section 11.3.1](#).

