12. DEFINITIONS, RECORDING, AND REPORTING OF ADVERSE EVENTS

12.1. Definition of Adverse Events

According to International Conference on Harmonization (ICH) guidance E2A, Clinical Safety Data Management: Definitions and Standards for Expedited Reporting, an adverse event (AE) is any untoward medical occurrence in a patient or clinical investigation patient administered a pharmaceutical product and which is not necessarily required to have a causal relationship with this treatment. An AE can therefore be any unfavorable and unintended sign (including an abnormal laboratory finding, for example), symptom, or disease temporally associated with the use of a medicinal product, whether or not considered related to the medicinal product.

A treatment-emergent AE (TEAE) is an AE that either commenced following initiation of study treatment or was present prior to study treatment but increased in frequency or severity following initiation of study treatment.

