### 10.1 Adverse Events

All AEs, treatment-emergent adverse events (TEAEs), and SAEs will be coded using MedDRA, version 21.0.

TEAEs are defined as either new onset AEs with an onset at the time of or following the start of treatment through ten days after the last dose of study medication, or a recurrence of an AE (or medical history) present prior to randomization but increasing in severity, frequency or relationship at the time of or following the start of treatment

An AE summary table will be presented for the following:

- TEAEs by severity

- TEAEs leading to study drug discontinuation
- TEAEs by relationship
- SAEs
- Oral Cavity AEs

Summaries of incidence rates (frequencies and percentages) of individual AEs by MedDRA SOC and preferred term will be prepared. Such summaries will be displayed for all TEAEs, TEAEs by maximum severity, and TEAEs by strongest relationship to study drug.

Each participant will be counted only once within each summation level (SOC; preferred term). If a participant experiences more than one TEAE within each summation level only, the TEAE with the strongest relationship or the maximum severity, as appropriate, will be included in the summaries of relationship and severity.

Additionally, a summary of the Oral Cavity AE characteristics will be presented; this includes information such as temporal proximity to the dose, duration and whether the AE was present the following morning.

Adverse events of special interest pertaining to abuse potential (as defined in the January 2017 Assessment of Abuse Potential for Drugs – Guidance for Industry) will be analyzed separately by treatment group, SOC and preferred term, and displayed in tabular format.

In the AE data listings, all AEs will be displayed. AEs that are treatment-emergent will be flagged.

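### SAP 7.3.1 sorts AEs by whether they started before the first dose, so a pre-dose AE that worsens on treatment can miss the TEAE tables where SAP 10.1 and protocol 12.1 place it

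*SAP*

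**What the plan says.** Three places bear on which AEs count as treatment-emergent.

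- **SAP 7.3.1** opens with a scope sentence: "To handle missing or partial AE and prior/concomitant medication dates, the following rules will be applied". After the rules for partial dates it adds a classification rule. AEs are split into pre-treatment and treatment-"emergent adverse events based on the response to the CRF question" on whether the event began before the first dose. The sentence is worded for AEs in general.
- **SAP 10.1** defines a TEAE by two limbs. The first is a new event "with an onset at the time of or following the start of treatment through ten days after the last dose of study medication". The second is "a recurrence of an AE (or medical history) present prior to randomization but increasing in severity, frequency or relationship" once treatment has started.
- **Protocol 12.1** also has two limbs: an event that began after treatment started, or one that "was present prior to study treatment but increased in frequency or severity following initiation of study treatment". It sets no end of window.

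On collection, protocol 11.3.1 says: "Patients will be monitored for AEs throughout the study from the time that the patient signs an informed consent and onward". Screening lasts 7 to 21 days and can include washout of earlier medication (protocol 7.1), and AEs are assessed at Visit 2 before randomization (protocol 10.2.1). SAP section 12 declares no change from the protocol.

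**The concern.** The 7.3.1 rule looks only at when an event started. The two definitions also look at what happened to it afterwards. For an event that started before dosing and got worse on treatment, the SAP therefore contains two rules with opposite answers, and no statement of which one a programmer should follow.

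The TEAE flag decides who is counted in the main AE incidence tables by SOC and preferred term, in the tables by maximum severity and by strongest relationship (SAP 10.1), and in the summary of TEAEs leading to discontinuation (SAP 10.1.1). Safety is the trial's only secondary objective. Two programmers who each follow a stated rule could deliver different tables. One visible symptom would be a participant shown in the disposition table as withdrawn for an AE but missing from the TEAE discontinuation summary, because that AE began during screening.

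**Working it through.** The plan gives no figure to reproduce and no AE counts, so no arithmetic applies. The check is to run each type of event through the three rules.

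| Event | SAP 7.3.1 (CRF question) | SAP 10.1 | Protocol 12.1 |
|---|---|---|---|
| (a) Starts after first dose, no later than ten days after last dose | TEAE | TEAE | TEAE |
| (b) Starts before first dose, does not worsen | Pre-treatment | Not a TEAE | Not a TEAE |
| (c) Starts between consent and first dose, worsens on treatment, stays on its original record | **Pre-treatment** | **TEAE** | **TEAE** |
| (d) As (c), but a new record is opened with a start date at worsening | TEAE (new record) | TEAE | TEAE |
| (e) Medical-history condition, first entered as an AE when it worsens on treatment | TEAE, if the start date is the date of worsening | TEAE | TEAE |
| (f) Starts more than ten days after last dose | **TEAE** | **Not a TEAE** | **TEAE** |

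1. Rows (a) and (b) agree throughout, so most AEs are unaffected.
2. Row (c) is the main conflict. The CRF answer is yes, which makes the event pre-treatment. Both definitions make it a TEAE through their worsening limb: SAP 10.1 has "present prior to randomization but increasing in severity, frequency or relationship at the time of or following the start of treatment", and protocol 12.1 says the same for frequency or severity.
3. Row (d) is the same clinical event with a different recording habit, and the conflict disappears. Whether (c) or (d) applies depends on how sites record worsening. The fields in protocol 11.3.1 are onset, resolution, severity, seriousness, causality, actions and outcome. No date of worsening is listed, and neither document says in general whether worsening opens a new record.
4. Row (e) shows that worsened medical history is mostly safe under 7.3.1, provided the AE start is entered as the date of worsening.
5. Row (f) is a separate mismatch. Here 7.3.1 agrees with protocol 12.1, and SAP 10.1 is the odd one out because of its ten-day limit.
6. Can row (c) occur? Yes. AEs are collected from consent, and screening normally runs 7 to 21 days.
7. What would be lost? Row (c) events would leave every table built on TEAEs. They would stay in the AE listings, which show all AEs (SAP 10.1), in the listing of AEs leading to discontinuation (SAP 10.1.1), and, if serious, in the SAE summary, which is not restricted to TEAEs (SAP 10.1.2).

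**The case against.** The best defence is that 7.3.1 was never meant to define a TEAE. It is a section of handling conventions that begins with missing and partial dates, and the CRF sentence comes straight after the imputation rules. Those rules can move a partial start date onto the first-dose date, so a direct question about onset is useful there. Section 10.1 is the place where the term is defined, and it agrees with the protocol on worsening. On this reading the two sections fit together.

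That is a plausible account of the intention, but the text does not say it. The CRF sentence is not confined to missing dates, whereas the medication rule that follows it is expressly confined to medications with missing start or stop dates. Nothing names 10.1 as the governing text.

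Other parts of the defence do stand, and they limit the point:

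- A reader might infer that every pre-existing event that worsens is dropped, so that TEAE incidence must be understated. The documents do not support this. If sites open a new record on worsening, few or no events are lost.
- A reader might point to insomnia, anxiety or suicidal ideation emerging during washout as the obvious casualties. These are weak examples. PTSD symptoms are reported as AEs only when they significantly worsen or become more frequent (protocol 11.3.1), so worsening on treatment would normally first be entered after dosing. Post-baseline suicidal ideation has its own reporting instructions (protocol 11.3.3), and on-treatment C-SSRS results are tabulated whatever the TEAE flag (SAP 10.3).
- A reader might assume the repair can be programmed from fields already collected. With no worsening date among the fields protocol 11.3.1 lists, that is not assured.
- The late-event mismatch is marginal. Visit 6 is the last scheduled visit, and early-termination participants are followed only for an ongoing AE or other condition (SAP 7.1). A late termination visit after a lapse in medication is possible (protocol 10.5.1), but few such events would be collected.

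**Conclusion.** The inconsistency is real but narrow. As written, SAP 7.3.1 gives the wrong class, by the SAP's own definition and the protocol's, to an AE that starts between consent and first dose, worsens on treatment and stays on its original record. Such an event would be missing from the TEAE tables but not from the listings or the SAE table. The mismatch for events beginning more than ten days after the last dose is secondary, and lies between SAP 10.1 on one side and 7.3.1 and the protocol on the other.

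The size cannot be computed. It depends on how many AEs start before dosing and worsen later, and on an unstated recording convention that could bring the loss close to zero. The conclusion assumes only that 7.3.1 is applied as worded. It is worth correcting because the affected outputs are the main safety tables and the ambiguity can be removed cheaply before unblinding.

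**What to change.** 1. In SAP 7.3.1, state that TEAE status is determined by the definition in section 10.1, and remove the CRF question as the classifier.
2. Keep the CRF question for one purpose: settling whether onset came before or after the first dose when the start date is missing, partial or the same day as that dose.
3. State the recording rule: on-treatment worsening of an AE that began before dosing is entered as a new record, or as a severity change, dated at worsening and flagged as a TEAE.
4. Reconcile the ten-day limit, and the relationship criterion that SAP 10.1 adds, with protocol 12.1, or list both in SAP section 12 as departures from the protocol.

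Items 1, 2 and 4 cost only SAP wording. Item 3 is the small downside: it needs an instruction to sites, and possibly a CRF field, because protocol 11.3.1 lists no worsening date. If AE pages are already complete, a blinded query limited to AEs that began before the first dose and were still ongoing then would cover the events at risk.

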## **8. STUDY PARTICIPANTS AND DEMOGRAPHICS**

### **8.1 Disposition of Participants and Withdrawals**

The numbers and percentage of participants randomized, completing the study, and withdrawing from the study, along with reasons for withdrawal, will be tabulated overall and by treatment group. The number and percentage of participants in each analysis population will be reported. This summary will be based on all participants who have data entered into the database.

### **8.2 Protocol Deviations**

Protocol deviations will be checked on complete data for all participants, determined during a (blinded) data review meeting before database lock, unblinding, and the final analysis.

Protocol deviations will be summarized by type and by treatment group for the Safety population. Protocol “violations” are not differentiated from deviations; instead, each deviation is identified either as “major” or “minor” depending upon its potential impact upon the integrity of the study data or the participant’s well-being.

Individual participants with protocol deviations will be listed.

### **8.3 Demographics and Other Baseline Characteristics**

Descriptive summaries of the demographic and other baseline characteristics will be completed for all participants in the safety population by treatment groups, unless otherwise specified.

Descriptive summaries of demographic and other baseline conditions will include:

- Demographics (age, gender, race/ethnicity, height, weight, body mass index (BMI), family status, education, presence of current major depressive episode (MDE), current nicotine, alcohol and THC usage, and employment status). In addition to the safety population, these will also be repeated for all randomized participants and the mITT population.
- Psychiatric history (MINI 7.0.2)
- Clinician administered scales
  - C-SSRS-Baseline/Screening Version
  - CA-AF
  - CAPS-5 Assessment (Diagnostic version)

Other assessment's baseline values will be reported with their respective follow-up measures.

Medical History will be coded using Medical Dictionary for Regulatory Activities (MedDRA) version 21.0 and summarized by System Organ Class (SOC) and Preferred Term using frequency counts by treatment group.

## 9. EFFICACY ANALYSES

### 9.1 Primary Efficacy Analysis Approach

The mean change from baseline in the CAPS-5 total score after 12 weeks of treatment in the TNX-102 SL 5.6 mg and placebo arms will be analyzed using a restricted maximum likelihood (REML) based repeated measures approach, including multiple imputation for missing values, accounting for the interim analysis. The model will include all participants in the mITT population. The dependent variable will be the observed change from baseline in CAPS-5 total score at each post-randomization visit.

#### 9.1.1 Primary Efficacy Analysis

An adaptive group sequential design will be performed for sample size adjustment or futility stop. To assure independence of the stage wise test statistics, the first stage population is defined as all participants available for efficacy analysis in the interim analysis. The second stage population is defined as all participants randomized after the interim cut-off and participants randomized prior to the interim cut-off, who were not available for efficacy analysis in the interim analysis.

Participants that drop out or reach Week 12 by the time of the interim cut-off will be included into the interim analysis. If the study continues until full planned recruitment, participants who were randomized prior to the interim cut-off, but did not drop out or reach Week 12 by the time of the interim cut-off, will be included into the second stage test statistic. Participants that were randomized after the interim cut-off will be included in the calculation of the second stage test statistic. Note that in every case, only participants that meet the mITT population criteria will be included.

Data of different stages will be combined using the inverse normal method to test the null hypotheses that there is no difference in the change from baseline in CAPS-5 total score between TNX-102 SL and placebo treatment groups at Week 12 ([Cui 1999](#)):

$$Z_1 = \Phi^{-1}(1 - p_1)$$

and  $Z_2 = w_1 Z_1 + w_2 \Phi^{-1}(1 - p_2)$

Where:

$Z_1$ = the Z statistic for the first stage

$Z_2$ = the combination test statistic at the end of the second stage

$w_i$ = the weighting applied for each associated Z statistic

$p_1$ = the first stage p-value

$p_2$ =the second stage p-value based on second stage participants

For maximum statistical efficiency, the weights are defined prospectively according to the square-root of the planned proportion of participants in the two stages, relative to the preplanned total enrollment of 250 participants, as  $w_i = \sqrt{0.5}$ . The calculation of these

weights is fixed and will not be changed due to unblinded data and is hence in line with the draft guidance on adaptive design clinical trials ([CDER, CBER, February 2010](#)). In order to control the type-I error, adaptive changes of the stage wise sample sizes will not lead to changes of the weights ([Lehmacher & Wassmer 1999](#)).

A Mixed Model Repeated Measures (MMRM) analysis will be performed for the change from baseline in CAPS-5 total score to estimate the treatment difference at Week 12. The model will include all participants in the mITT population, and the dependent variable will be the observed change from baseline in CAPS-5 total score at each post-randomization visit. Covariates in the model will include the fixed categorical effects of treatment, site, sex, and treatment by visit interaction, as well as the continuous fixed covariates of baseline score and baseline score by visit interaction. An unstructured covariance matrix will be used to model the within-subject variance-covariance errors. The Kenward-Roger approximation will be used to estimate the denominator degrees of freedom. Should the unstructured model fail to converge, an autoregressive AR(1) covariance structure will be attempted, then finally compound symmetric should AR(1) not converge.

Missing data for participants in the mITT population will be imputed via multiple imputation (MI) ([Carpenter, 2013](#); [Mallinckrodt, 2013](#)). Ten repeats of the imputation will be performed using Markov Chain Monte Carlo (MCMC) assuming non-monotone missing. Where the study medication was discontinued due to lack of efficacy, lost to follow-up, or to an AE, missing values will be imputed drawing from the baseline values, conditioned on the non-missing post-baseline values, of all participants in the mITT population under the assumption that they are missing not at random (MNAR); covariates will include site and sex. If the study medication was discontinued for any other reason, values will be imputed within treatment group using MI under the assumption that they are missing at random (MAR) with covariates for site, sex, and the CAPS-5 score recorded at each time point (including baseline). The MAR approach will also be applied for sporadic missing values (prior to discontinuation).

The test statistic based upon the least squares (LS) mean treatment difference and associated p-value [REDACTED] will be presented for each stage.

In addition, the least squares means and 95% confidence intervals (CIs) will be calculated for the treatment difference between TNX-102 SL and placebo at each time point.

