13.6. Interim Analyses

An interim analysis will be performed once approximately 50% of the planned patients have enrolled and those patients have either completed or discontinued the study. The purpose of the interim will be to potentially increase the sample size to maintain statistical power conditioned on the results of the first 50% of patients; or stop the study for futility if the conditional power is

sufficiently low. The study team will only be informed of the recommendation to maintain the original sample size, increase the sample size (by a fixed, pre-specified amount) or discontinue the study (at which point unblinding would occur).

For the primary and key secondary outcomes, the results from before and after the interim will be combined with Cui, Hung, Wang (CHW) methodology ([Cui, 1999](#)). Full details of the interim analysis procedure and steps to maintain treatment blinding of the study team will be described in the SAP and the IDMC Charter and finalized prior to execution of the interim analysis.

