## 4. ANALYSIS AND REPORTING

### 4.1 Interim Analysis

An interim analysis will be performed when approximately 50% of the initially planned enrollment is evaluable for efficacy assessments. This interim analysis will be performed by an unblinded team separate from the team responsible for the conduct and analysis of the study. An Independent Data Monitoring Committee (IDMC) will review the data and recommend to the Sponsor to increase the sample size by a fixed amount, keep the current sample size and continue, or stop the study early for futility in the event the conditional power is <20%. If the IDMC recommends an increase in sample size, the maximum increase will be limited to 120 additional participants in blocks of 10 participants. If the conditional power is at or over 85% with the current sample size, then the IDMC will recommend continuing at the current sample size; if it is between 20% and <85%, the IDMC will recommend increasing the sample size. The increase will be chosen with the goal of increasing the sample size by the minimum number of subjects sufficient to raise the conditional power to at least 90%. If the conditional power at the current sample size is over 20% and the maximum increase of 120 subjects falls short of raising the conditional power to at least 90%, the committee will recommend an increase of 120 subjects. No further information will be provided to the sponsor beyond this recommendation.

The interim analysis will be conducted approximately 16 weeks after randomization of approximately 125 participants, i.e. when approximately 50% of the initially planned participant enrollment (250) is evaluable for efficacy assessments (approximately 12 weeks); and related data cleaning, database freeze, and administrative tasks have been completed on this cohort (approximately 4 weeks).

In case the study is stopped early for futility, participants will be managed according to a study termination plan.

In the case of an early stop for futility, initial results may be released prior to full database lock; however, clinical study report (CSR) results will be based on the final analysis described below.

Conditional power will be calculated using the following formula ([Mehta, 2010](#)):

$$CP(Z_1, \check{n}_2) = 1 - \Phi \left( \frac{Z_{\alpha} \sqrt{n_2} - Z_1 \sqrt{n_1}}{\sqrt{\check{n}_2}} - \frac{Z_1 \sqrt{\check{n}_2}}{\sqrt{n_1}} \right)$$

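### SAP 9.1.1 places recently randomized participants in stage 1 only if they drop out, so interim stage depends on a post-randomization outcome and departs from the enrolment cohort in Protocol 13.6 and SAP 4.1

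*SAP*

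**What the plan says.** SAP 9.1.1 assigns stage by what has happened to a participant when the interim data are cut: "Participants that drop out or reach Week 12 by the time of the interim cut-off will be included into the interim analysis". Participants already randomized by that date "but did not drop out or reach Week 12 by the time of the interim cut-off, will be included into the second stage test statistic". Those randomized after it are also in stage 2, and everyone must meet the mITT definition. The section gives independence of the stage statistics as its reason. It does not define the cut-off date.

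Protocol 13.6 places the interim "once approximately 50% of the planned patients have enrolled and those patients have either completed or discontinued the study" and ties the decision to the results of that first half. SAP 4.1 gives the timing: "The interim analysis will be conducted approximately 16 weeks after randomization of approximately 125 participants". That is about 12 weeks of follow-up plus about 4 weeks, by the end of which "related data cleaning, database freeze, and administrative tasks have been completed on this cohort". SAP 4.1 also describes the trigger as about half of planned enrolment being evaluable for efficacy. SAP 12 declares no changes from the protocol.

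Two other provisions decide whether this matters:
- Under SAP 4.1 the IDMC may recommend to "stop the study early for futility in the event the conditional power is <20" percent, and it recommends a larger sample when conditional power is from 20% to below 85%.
- Under the imputation rules in SAP 9.1.1, after discontinuation for lack of efficacy, loss to follow-up or an AE, "missing values will be imputed drawing from the baseline values, conditioned on the non-missing post-baseline values". For the rest: "If the study medication was discontinued for any other reason, values will be imputed within treatment group", under MAR.

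**The concern.** Take two participants randomized on the same day, six weeks before the cut-off. One drops out in week 5 with a post-baseline CAPS-5 and enters stage 1. The other continues and enters stage 2. A post-randomization outcome, not enrolment order, has decided the stage. If recruitment continues during the 12-week wait, stage 1 is enriched for dropouts and stage 2 is depleted of them.

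Because dropouts for three of the listed reasons are imputed from baseline values, dropout share feeds into the stage estimate. The two stages then do not estimate the same quantity. The first-stage statistic Z1 drives both the futility recommendation and the sample-size increase, and a futility stop, once acted on, cannot be undone. The set analysed is also not the one that Protocol 13.6 describes.

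**Working it through.** **1. The plan's own figures reproduce.** Half of 250 is 125; 12 + 4 = 16 weeks; each stage weight is √(125/250) = √0.5 = 0.7071. The SAP 4.1 conditional power formula with n1 = 125, n2 = 250 and 1.96 (two-sided 0.05, Protocol 13) reduces to CP = 1 − Φ(1.96√2 − 2·Z1). CP is 20% at Z1 = 0.965 and 85% at Z1 = 1.904.

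**2. Who is in stage 1**, with the cut-off taken as 12 weeks after the 125th randomization:

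| Participant | SAP 9.1.1 | First-125 cohort |
|---|---|---|
| Among the first 125 | Stage 1 | Stage 1 |
| Randomized later, dropped out before the cut-off | Stage 1 | Stage 2 |
| Randomized later, still on study at the cut-off | Stage 2 | Stage 2 |

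The definitions differ only in the second row.

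**3. How many move.** Accrual and dropout are assumed. With r patients a week, 12-week dropout d spread evenly in time, and all dropouts in mITT, the overlap is 12r and the expected number moved is k = 12r × d/2.
- r = 5, d = 20%: k = 60 × 0.10 = 6. Stage 1 has (25 + 6)/131 = 23.7% dropouts; stage 2 has (50 − 31)/119 = 16.0%.
- r = 3, d = 10%: k = 1.8; shares 11.3% and 8.7%.
- r = 10, d = 30%: k = 18; shares 38.8% and 18.2%.

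These k are upper figures. Protocol 10.5.1 schedules no CAPS-5 at an early termination visit before Day 11, so some dropouts fail mITT.

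**4. Effect on the estimate.** Assume completers improve by 16 points on active and 10 on placebo (effect 6, SD 12) and dropouts do not change. With dropout shares a (active) and p (placebo), the stage effect is 16(1 − a) − 10(1 − p) = 6 − 16a + 10p. With equal shares this is 6(1 − share). Enrichment lowers the stage 1 effect unless the rise in p exceeds 1.6 times the rise in a; beyond that it reverses.

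**5. Simulation**: 12,000 trials per scenario on these assumptions, with exponential dropout, pre-Day-11 dropouts excluded, a two-sample Week 12 test per stage, the SAP 4.1 sample-size rule, and the futility boundary held at Z1 = 0.965 for both definitions. At 25% dropout per arm, 5.8 (5/week) or 9.3 (8/week) dropouts move. Stage 1 dropout share goes from 22% to 26% or 28%, and stage 2 from 22% to 18% or 16%. The formula in step 4 gives 6 × 0.72 = 4.32 and 6 × 0.84 = 5.04 at 8/week, against the simulated 4.30 and 5.06.

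Probability that conditional power is below 20%:

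| Dropout active/placebo | Dropouts at no change | SAP 9.1.1, 5/week | SAP 9.1.1, 8/week | First 125 |
|---|---|---|---|---|
| 25%/25% | all | 18.8% | 19.7% | 17.3% |
| 25%/25% | 60% | 11.5% | 11.6% | 11.1% |
| 30%/22% | all | 33.8% | 36.0% | 29.6% |
| 30%/22% | 60% | 17.7% | 18.5% | 16.5% |
| 20%/35% | all | – | 4.9% | 5.4% |
| 10%/30% | all | – | 1.1% | 1.7% |

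Stage 1/stage 2 effects:
- 25%/25%, all at no change: 4.42/4.90 (5/week) and 4.30/5.06 (8/week), against 4.64/4.66.
- 10%/30%, all at no change, 8/week: 7.41/6.95 against 7.22/7.25.
- All dropouts MAR, 8/week: 5.95/6.00 under both definitions.

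Power in the first row is 76.2% and 75.5% against 76.9%; in the second, 85.9% and 85.8% against 86.1%.

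**6. Check on other assumptions.** A simpler simulation (overall difference 4 points, all dropouts in mITT at no change, actual n1 in the conditional power formula) gave P(CP < 20%) of 28.7% against 25.6% at 20%/20% and 5/week. At 30%/20% and 10/week it gave 42.6% against 27.9%, with stage effects 3.10/5.12 against 4.03/4.01.

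**7. Type I error.** With no effect and equal dropout, the one-sided error in the step 5 simulation, ignoring the futility stop, was 2.6% against 2.7% (Monte Carlo SE 0.15 points). In the simpler simulation, including unequal dropout, it was 2.4–2.8% against 2.5–2.7%.

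**The case against.** The strongest reply has four parts.

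**The texts can be read together.** SAP 4.1 speaks of participants evaluable for efficacy, which fits SAP 9.1.1, and Protocol 13.6 mainly sets a trigger and defers details to the SAP and IDMC Charter. The evaluable wording does soften the clash with SAP 4.1. It does not remove it, because the same section times the interim from about 125 randomized and treats them as a cohort. Protocol 13.6 also says whose results the decision uses.

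**The larger shifts need every dropout at no change, which is not the planned imputation.** This stands. Withdrawal of consent, non-compliance and other reasons are MAR, early termination scores are kept at the nearest visit (SAP 7.1.2), and the simulation replaces the MMRM with a two-sample test. The 60% rows show much smaller shifts, and the direction depends on the dropout pattern.

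**The test remains valid.** Agreed. Each participant is in one stage, the weights are fixed, and no material inflation appeared. The objection is to what Z1 measures. It is also true that the IDMC only recommends.

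**The rule uses all final outcomes and was written for independence.** Enrolment order gives disjoint stages equally well, provided the interim comparison excludes later-randomized participants. SAP 9.1.1 already makes stage 1 the interim analysis set, so this is a point to state, not an obstacle.

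**Conclusion.** The concern holds. On the text, SAP 9.1.1 lets dropout decide the stage for anyone randomized less than 12 weeks before the cut-off, and the resulting stage 1 is not the cohort in Protocol 13.6 or the 125 in SAP 4.1.

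The size is conditional and mostly modest. On the assumed inputs, the probability of falling below the futility threshold rises by 0.4 to 2.4 points with equal 25% dropout (11.1% to 11.5% at least, 17.3% to 19.7% at most). With 30%/22% dropout it rises by 1.2 to 6.4 points (16.5% to 17.7%, 29.6% to 36.0%). It does not arise if accrual pauses, the effect shift is absent if dropouts are MAR, and it reverses if placebo dropout is sufficiently higher. Final power moves by at most 1.4 points in the 25%/25% scenarios with the sample-size rule (76.9% to 75.5%), and type I error is not the issue. All sizes rest on assumed accrual, dropout, effect and SD, and on a cut-off 12 weeks after the 125th randomization, inferred from SAP 4.1. This should be changed because it affects an irreversible decision and costs almost nothing to correct.

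**What to change.** In SAP 9.1.1, define stage 1 as the first approximately 125 participants by randomization order who meet mITT, each followed to Week 12 or discontinuation, with the exact number fixed before the cut-off. Put every later-randomized mITT participant in stage 2, whatever their status at the cut-off. Define the cut-off date, say that the interim comparison uses stage 1 participants only, and align the wording with SAP 4.1 and Protocol 13.6.

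The stages stay disjoint, expected dropout share becomes the same in both under constant dropout rates, and the √0.5 weights still match the planned 125/125 split. The cost is one SAP paragraph. No patients, time or data are added, because SAP 4.1 already waits about 12 weeks after roughly the 125th randomization.
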